6.4 BASELINE PERIOD

The Baseline Period begins at enrollment and ends at the start of the SCD Treatment Period (when the subject starts treatment). The following information will be recorded as close to the start of the SCD Treatment Period as possible. Data from standard of care tests may be used as baseline data, as long as it is captured within the time frames noted.

- **Demographic Data**
 - a) Date of birth
 - b) Gender
 - c) Race/ethnicity
- **Hospitalization Data**
 - a) Hospital Admission Date
 - b) Hospital Admission Diagnosis
 - c) ICU Admission Date
 - d) ICU Admission Diagnosis
 - e) Medical History
- **Vital Signs/Physical Assessment (within 12 hours prior to the start of SCD Treatment Period unless otherwise indicated)**
 - Temperature
 - Blood Pressure and heart rate
 - Body weight at ICU admission
 - PRISM II Score
 - Physical Exam
 - Urine Output (previous 24 hours)
 - ICU percent fluid overload at CRRT initiation (Defined as [(Fluid In (liters) – Fluid Out (liters))/ICU admission weight (kg)] x 100% where Fluid In and Fluid Out are calculated from ICU admission to CRRT initiation.
- **Clinical Laboratory Tests (within 12 hours prior to the start of SCD Treatment Period)**
 - CBC with differential
 - BUN/Creatinine
 - Na, K, Cl, HCO₃, Ca, Mg, Ionized Ca, PO₄
 - ALT, AST, Bilirubin, ALP, Total Protein, Albumin, Glucose
- **Respiratory**
 - Status – Ventilator support (yes/no; date of intubation)
 - If on Vent: FiO₂
 - If on Vent with an arterial line: Arterial Blood Gas (12 hours prior to start of SCD Treatment Period)
 - If on Vent without an arterial line: Arterial Blood Gas (if available within 12 hours of start of Observation Period per standard of care)
 - ECMO Status (yes/no; date of cannulation)
- **Blood for Research**
 - Blood sample should be collected within 6 hours before the start of the SCD Treatment Period

- Blood sample will be sent to an outside laboratory for testing of biomarkers. The research laboratory is Innovative BioTherapies located at [name].
- **Other (Event-driven)**
 - Acknowledgement (yes/no) to critical medications, vasopressors, and blood products administered to the patient in the 24 hours prior to start of SCD Treatment Period
 - Adverse Events occurring since enrollment
 - Microbiology/culture data (within the last 72 hr.)

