6.3 SCD SCHEDULE OF EVENTS

	Pre-SCD	SCD TREATMENT PERIOD ¹										POST SCD PERIOD ²			Day 28 ³	Day 60 ³
		Hr 0-24	Hr 24-48	Hr 48-72	Hr 72-96	Hr 96-120	Hr 120-144	Hr 144-168	Hr 168-192	Hr 192-216	Hr 216-240	Hr 0-24	Hr 24-48	Hr 48-72	Hr 72-96	Hr 96-120
Vital Signs / Physical Assessment																
ICU Admission Weight	X															
Temperature, BP, Heart Rate	X	X	X	X	X	X	X	X	X	X	X	X	X	X	X	X
Daily Fluid Balance and Urine Output	X	X	X	X	X	X	X	X	X	X	X	X	X	X	X	X
Blood Product Administration	X	X	X	X	X	X	X	X	X	X	X	X	X	X	X	X
Critical Medications	X	X	X	X	X	X	X	X	X	X	X	X	X	X	X	X
Physical Exam by Investigator	X											X				
PRISM II Score	X															
Sepsis Assessment	X															
Fluid Overload at SCD Initiation	X															
Microbiology / Culture Data	X	X	X	X	X	X	X	X	X	X	X	X	X	X	X	X
Concomitant Treatments or Procedures	X	X	X	X	X	X	X	X	X	X	X	X	X	X	X	X
Laboratory Testing																
CBC with differential	X	X	X	X	X	X	X	X	X	X	X	X				
Creatinine	X	X	X	X	X	X	X	X	X	X	X	X	X		X	X
BUN, Na, K, Cl, HCO ₃ , Ca, Mg, PO ₄ , iCa	X	X	X	X	X	X	X	X	X	X	X	X	X			
ALT, AST, Bilirubin, ALP, TP, Albumin, Glucose	X	X	X	X	X	X	X	X	X	X	X					
Blood for Research Biomarkers ⁴	X		X		X		X		X		X				X	
Cardiorespiratory Assessment																
Ventilator Use and Settings	X	X	X	X	X	X	X	X	X	X	X	X	X	X	X	X
Arterial Blood Gas ⁸	X	X	X	X	X	X	X	X	X	X	X	X	X			
Vasopressors Administered	X	X	X	X	X	X	X	X	X	X	X	X	X	X	X	X
ECMO	X	X	X	X	X	X	X	X	X	X	X	X	X	X	X	X
Renal Replacement and SCD																
Post Filter iCa	X ⁵	X ^{6,7}	X ⁷													
SCD Filter Change, Q24Hr ± 4Hrs		X	X	X	X	X	X	X	X	X	X					
CRRT Settings and Other RRT Use	X	X	X	X	X	X	X	X	X	X	X	X	X	X	X	X
CRRT Device and SCD Performance	X	X	X	X	X	X	X	X	X	X	X					
Other – Event Driven																
Adverse Events	X	X	X	X	X	X	X	X	X	X	X	X	X	X	X ⁹	X ⁹

¹SCD Treatment Period lasts 240 hours or until termination criteria are met per Section 7

²The Post SCD Period lasts 120 hours or until ICU discharge, whichever comes first

³Window for follow up visits is day from SCD initiation +7 days

⁴Blood for research biomarkers should be completed before SCD initiation (or 6 hours prior), as well as 48h, 96h, 144h, 192h, end of SCD, and 120 hours post SCD \pm 6 hours

⁵Post filter iCa only need recorded in the pre-SCD time period if patient was on CRRT with RCA prior to SCD initiation

⁶Post filter iCa should be obtained Q1Hr \pm 30min until <0.40 mmol/L for two consecutive measurements within the first 12 hours of SCD

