6.5 SCD TREATMENT PERIOD

The SCD Treatment Period begins when the subject starts treatment and will continue up to a maximum of 240 hours from the time of Treatment Start. A subject may begin CRRT therapy and SCD treatment at the same time, which would also mark the beginning of the SCD Treatment Period.

This treatment period has been broken into ten 24 hour time periods. It ends when the subject has reached 240 hours in the treatment period or when the subject meets the termination criteria outlined in **Section 7.2** as determined by the Principal Investigator or Medical Team at the participating Clinical Site.

All tests are scheduled on a 24 hour cycle, or once a day, and can be scheduled to be drawn around each participating site's ICU blood drawing schedule, with the exception of any test that requires a specific draw frequency.

The following information will be obtained for subjects enrolled during the SCD treatment period on a daily basis unless otherwise specified:

- **Vital Signs/Physical Assessment**
 - Temperature
 - Blood Pressure, heart rate
 - Urine Output (previous 24 hours)
 - Net Fluid Balance (previous 24 hours)
- **Clinical Laboratory Tests**
 - CBC with differential
 - BUN, Creatinine
 - Na, K, Cl, HCO₃, Ca, ionized Ca, Mg, PO₄
 - ALT, AST, Bilirubin, ALP, Total Protein, Albumin, Glucose
- **Respiratory**
 - Status – Ventilator support (yes/no; date of intubation or extubation, as applicable)
 - If on Vent: FiO₂
 - If on Vent with an arterial line: Arterial Blood Gas

- If on Vent without an arterial line: Arterial Blood Gas (if completed as standard of care)
- ECMO Status (yes/no; date of cannulation or decannulation as applicable)
- **Blood for Research**
 - Collect at hours 48, 96, 144, 192 and end of SCD treatment (\pm 6 hours). Blood for biomarkers will be collected as close as possible to the time of SCD scheduled changes in the days required (\pm 6 hours) if practical and within window.
 - Blood sample will be sent to an outside laboratory (Innovative Therapies) for testing of biomarkers
- **CRRT Parameters (Start at hour 0)**
 - Parameters include modality, blood flow rate, net fluid removal, dialysate or replacement solution flow rate, citrate infusion rate, calcium replacement rate.
 - System performance (circuit survival - event driven)
 - Post filter ionized calcium

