6.6.2 DAY 28 POST ENROLLMENT

This visit may be done via telephone call or office visit. Please record the following information on day 28 (+7 days) following enrollment:

- Presence / date and setting of mechanical ventilation (since last visit)
- Presence / date and settings of renal replacement therapy (since last visit)
- Serious Adverse events (since last visit)

- Serum creatinine (if an office visit takes place)
- ICU discharge date
- Hospital discharge date

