6.6.3 DAY 60 POST ENROLLMENT

This visit may be done via telephone call or office visit. Please record the following information on day 60 (+7 days) following enrollment:

- Presence / dates of mechanical ventilation (since last visit)
- Presence / dates of renal replacement therapy (since last visit)
- Serious Adverse events (since last visit)
- Serum creatinine (if an office visit takes place)

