The Prospective Pediatric CRRT (ppCRRT) database will be used as a control for the CRRT treatment related factors including: patient age, gender, primary cause of AKI, total treatment duration, CRRT modality (CVVH, CVVHD, CVVHDF), CRRT small solute clearance (ml/1.73m²/hour), baseline estimated GFR (using the original Schwartz formula, which was used in the ppCRRT), urine output in the 24 hours prior to CRRT initiation (ml/kg/hour), percent fluid overload at CRRT initiation based on admission ICU weight, vasoactive medication number at time of CRRT initiation and mean airway pressure at CRRT initiation.

An additional analysis will also evaluate patients who have achieved targeted iCa levels during 90% of treatment time and those who do not.

In summary this protocol meets all criteria necessary for clinical scientific inquiry related to a test of hypothesis in a well monitored environment focused on subject safety during the conduct of the study. Basic statistics will be performed on the data sets along with historical data comparisons and subjected to subset analysis where appropriate. The results will help to guide the design of a future pivotal study of this device.

The rational for therapy, study objectives and endpoints, design, inclusion and exclusion criteria are explicitly defined. Subject safety parameters are well documented including safety reporting, safety observations and assays, procedures for subject withdrawal and study discontinuation criteria along with monitoring device integrity and performance. Lastly, a review of all prior SCD human study safety data is included in the protocol for full disclosure to study investigators and the informed consent document includes a full description of all known and potential risks of the device treatment.

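### The historical comparison has no common time zero: time already spent on CRRT before SCD is unhandled, and matching covariates with a stated time are anchored at different points in the two cohorts

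*Combined protocol and SAP*

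**What the plan says.** **The comparison.** Section 3.1 makes comparison with historic data on in-hospital mortality, and on mortality and dialysis dependency at days 28 and 60, part of the primary objective. The synopsis evaluation plan repeats it. Sections 3.2 and 12 name the ppCRRT Registry as the source of matched controls.

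**The SCD clock.** Section 6.6.2: "Please record the following information on day 28 (+7 days) following enrollment". Section 6.6.3: "Please record the following information on day 60 (+7 days) following enrollment". Footnote 3 of the Section 6.3 schedule instead counts the follow-up window from SCD initiation.

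**SCD-side covariates.** Section 6.4 collects vital signs, PRISM II and laboratories "within 12 hours prior to the start of SCD Treatment Period". Urine output in the same pre-SCD block covers the previous 24 hours.

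**Registry-side covariates.** Section 12 lists "percent fluid overload at CRRT initiation based on admission ICU weight" together with urine output before CRRT initiation, and vasoactive drug count and mean airway pressure at CRRT initiation.

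**Fluid overload.** The Section 6.3 row reads "Fluid Overload at SCD Initiation". Section 6.4 has "ICU percent fluid overload at CRRT initiation", which agrees with Section 12.

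**CRRT before SCD.** Footnote 5 of Section 6.3 asks for a pre-SCD calcium value "if patient was on CRRT with RCA prior to SCD initiation", so prior CRRT is foreseen. Section 6.5 also allows no lag at all: "A subject may begin CRRT therapy and SCD treatment at the same time". Sections 5.2 and 5.3 set no limit on prior CRRT. The 48 hours in Section 6.1 limits screening before enrollment, not time on CRRT.

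**The concern.** A child whose CRRT started before SCD can enter only if still alive and on CRRT when SCD begins. Unless controls meet the same condition, the two groups are selected differently: early deaths, and children who come off CRRT early, can appear among the controls but not in the SCD cohort. No section defines a common time zero, a landmark, delayed entry or matching on elapsed CRRT time.

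Covariate timing is a second problem. Section 6.2.2 states that starting CRRT can itself improve hemodynamics by correcting acidosis and low calcium, and Appendix A scores blood pressure, calcium and bicarbonate within PRISM II. A PRISM II score taken after some time on CRRT may therefore not mean the same as one taken at CRRT initiation, yet it is a matching variable. Urine output has the same difficulty, and here both anchors are documented.

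At stake is how the historical comparison is read. Section 12 says the results will help design a future pivotal study.

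**Working it through.** The plan states no sample-size, power or alpha figure for this comparison, so there is none to reproduce. The check sets the clocks side by side and then asks what a missing common origin can do.

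**1. Clocks**

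| Item | SCD children | Registry controls |
|---|---|---|
| Days 28 and 60 | Enrollment (6.6.2, 6.6.3) or SCD initiation (6.3, footnote 3) | Not stated |
| PRISM II | Within 12 h before SCD (6.4) | Matched; time not stated |
| Urine output | Previous 24 h, in the pre-SCD block (6.4) | 24 h before CRRT initiation (12) |
| Fluid overload | CRRT initiation (6.4) or SCD initiation (6.3 row) | CRRT initiation (12) |
| Duration of renal support | Initiation of renal replacement (3.2) | Not stated |

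**2. Clock restarted after a lag, no device effect**

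Inputs: control mortality D = 50% (approximate figure in the synopsis rationale), or 35% = 1 − 65% (the survival in Section 12, which applies only to the 201 of 370 registry children on CRRT for 1 to 7 days). Assumptions, because the documents give neither: lag L from CRRT start to SCD of 0 to 7 days, and a Weibull death hazard with shape k from 0.3 to 1.0.

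With H = −ln(1 − D) and S(t) = exp[−H(t/T)^k], apparent mortality over T days from SCD start is 1 − S(L+T)/S(L).

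Example: D = 0.50, T = 60, L = 2, k = 0.5. H = 0.693; (62/60)^0.5 − (2/60)^0.5 = 1.0165 − 0.1826 = 0.834; 1 − exp(−0.693 × 0.834) = 43.9%.

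| D | T (days) | L (days) | k = 1.0 | 0.7 | 0.5 | 0.3 |
|---|---|---|---|---|---|---|
| 50% | 60 | 2 | 50.0 | 47.5 | 43.9 | 36.2 |
| 50% | 60 | 7 | 50.0 | 44.8 | 39.1 | 29.7 |
| 50% | 28 | 2 | 50.0 | 46.1 | 41.3 | 32.5 |
| 35% | 60 | 2 | 35.0 | 33.0 | 30.2 | 24.4 |

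The artefact is nil with a constant hazard (k = 1) or zero lag. It favours SCD when the hazard falls over time.

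**3. Truncation with two exits, no device effect**

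Suppose that, before SCD would start, a fraction a die and a fraction b leave CRRT alive and go on to survive. Apparent mortality is (D − a)/(1 − a − b).

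- a = 0.10, b = 0: 0.40/0.90 = 44.4% for D = 50%; 0.25/0.90 = 27.8% for D = 35%.
- a = 0.10, b = 0.10: 0.40/0.80 = 50.0%; 0.25/0.80 = 31.25%.
- a = 0.05, b = 0.20: 0.45/0.75 = 60.0%; 0.30/0.75 = 40.0%.

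The result lies below D only if a/(a + b) > D. Otherwise the bias is nil or runs against SCD.

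**4. Sampling error.** With the maximum of 10 children, 3 deaths give an exact 95% interval of 6.7% to 65.2%.

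**5. With a common time zero.** If controls must be alive and on CRRT at the same elapsed time, apparent mortality with no device effect equals that of the controls so selected, and the artefact is zero in both illustrations.

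**The case against.** The strongest reply is that the documents do not show the bias to exist, still less to favour the device.

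- *The registry outcome date is unknown.* A reader might infer that control deaths are counted from CRRT initiation. That anchor is documented only for some covariates; the start of registry follow-up and the time of registry PRISM II scoring are never given. This stands. It makes the mismatch in outcome clocks a possibility and the missing definition the fault.
- *The direction is not assured.* A reader might infer that an inert device would necessarily look beneficial. Simultaneous starts carry no lag, a constant hazard gives no artefact in fixed windows, and loss of early recoverers pushes the other way. So could a PRISM II score improved by CRRT, by pairing a child with a less ill control. This stands too.
- *The registry's 65% survival does not yield a size.* It describes children with at least one day of CRRT, so stripping first-48-hour deaths from it is not coherent, and no passage supports a uniform 48-hour lag.
- *Total treatment duration is already a control factor (Section 12).* Matching on it would exclude some early deaths, but it is known only after treatment ends and does not reproduce being alive and on CRRT when SCD starts.
- *CRRT start must already be known.* The fluid-overload formula and the duration of renal support both need it. True, so the added data burden is small; Section 6.4 nonetheless lists no such field.
- *This is a pilot.* Up to 10 children are enrolled, and the plan disclaims power and an efficacy design. That limits the consequence, but the comparison remains in the primary objective.

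**Conclusion.** The point holds as a missing definition with a real consequence. For children whose CRRT preceded SCD, the plan as written leaves pre-SCD survival unhandled, and for urine output it would set a value taken before SCD against one taken before CRRT. The bias may favour SCD if early deaths dominate, but neither direction nor size can be determined from the documents. The figures in steps 2 and 3 rest on assumed lags, hazard shapes and exit fractions; they show what is possible and are not estimates. It would be wrong to conclude that SCD mortality will be understated, or to attach a number of percentage points to it.

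Sampling error with 10 children is likely to exceed the bias in most of these scenarios. It does not remove a systematic difference, and the remedy works in either direction. This is a change that should be made before the comparison is run.

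**What to change.** 1. Record the CRRT start date and time explicitly for every child, and report the interval from CRRT start to SCD start.
2. Select registry controls who were alive and still on CRRT at the same elapsed time from CRRT start as the matched child's SCD start.
3. Count Day 28 and Day 60 from that landmark in both groups, for mortality and for dialysis dependency. State the date from which registry follow-up runs.
4. Take matching covariates at CRRT initiation in both groups, and state when registry PRISM II was scored.
5. Do not use total treatment duration as a substitute; it is a post-baseline variable.
6. Reconcile the enrollment clock (6.6.2, 6.6.3) with the SCD-initiation clock (6.3, footnote 3), and the fluid-overload row in 6.3 with 6.4 and Section 12.

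The cost is one date/time field, retrieval of covariate values at CRRT initiation for children already on CRRT, and analysis wording. Treatment does not change. The downside is fewer eligible controls, on top of an already long matching list and a 10 to 20 kg weight range; the documents do not allow the loss to be estimated.

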6.5 SCD TREATMENT PERIOD

The SCD Treatment Period begins when the subject starts treatment and will continue up to a maximum of 240 hours from the time of Treatment Start. A subject may begin CRRT therapy and SCD treatment at the same time, which would also mark the beginning of the SCD Treatment Period.

This treatment period has been broken into ten 24 hour time periods. It ends when the subject has reached 240 hours in the treatment period or when the subject meets the termination criteria outlined in **Section 7.2** as determined by the Principal Investigator or Medical Team at the participating Clinical Site.

All tests are scheduled on a 24 hour cycle, or once a day, and can be scheduled to be drawn around each participating site's ICU blood drawing schedule, with the exception of any test that requires a specific draw frequency.

The following information will be obtained for subjects enrolled during the SCD treatment period on a daily basis unless otherwise specified:

- **Vital Signs/Physical Assessment**
 - Temperature
 - Blood Pressure, heart rate
 - Urine Output (previous 24 hours)
 - Net Fluid Balance (previous 24 hours)
- **Clinical Laboratory Tests**
 - CBC with differential
 - BUN, Creatinine
 - Na, K, Cl, HCO₃, Ca, ionized Ca, Mg, PO₄
 - ALT, AST, Bilirubin, ALP, Total Protein, Albumin, Glucose
- **Respiratory**
 - Status – Ventilator support (yes/no; date of intubation or extubation, as applicable)
 - If on Vent: FiO₂
 - If on Vent with an arterial line: Arterial Blood Gas

- If on Vent without an arterial line: Arterial Blood Gas (if completed as standard of care)
- ECMO Status (yes/no; date of cannulation or decannulation as applicable)
- **Blood for Research**
 - Collect at hours 48, 96, 144, 192 and end of SCD treatment (\pm 6 hours). Blood for biomarkers will be collected as close as possible to the time of SCD scheduled changes in the days required (\pm 6 hours) if practical and within window.
 - Blood sample will be sent to an outside laboratory (Innovative Therapies) for testing of biomarkers
- **CRRT Parameters (Start at hour 0)**
 - Parameters include modality, blood flow rate, net fluid removal, dialysate or replacement solution flow rate, citrate infusion rate, calcium replacement rate.
 - System performance (circuit survival - event driven)
 - Post filter ionized calcium

Therapy Initiation	Q 1 hr \pm 30min. until post filter iCa level <0.40 mmol/L; for two consecutive measurements within the first 12 hours of SCD then Q 6hr \pm 1hr.
After any Calcium or Citrate rate change	Q 1 hr \pm 30min. until post filter iCa level <0.40 mmol/L; then Q 6hr \pm 1hr.
After any Interruption: Recirculation, Procedure, Restart	Q 1 hr \pm 30min. until post filter iCa level <0.40 mmol/L; then Q 6hr \pm 1hr.

- **SCD Performance (Start at hour 0)**
 - SCD █ performance (event driven)
 - SCD and SCD Blood Tubing Set Change every 24 hour (\pm 4 hours)
- **Other (Event Driven)**
 - Acknowledgement (yes/no) to critical medications, vasopressors, and blood products administered to the patient
 - Adverse Events
 - Diagnostic/Therapeutic Procedures
 - Microbiology/culture data

6.6 STUDY FOLLOW UP PERIOD

6.6.1 POST SCD TREATMENT PERIOD

This Study Follow Up period has been broken into five 24 hour time periods. It starts when the subject has reached 240 hours in the treatment period or when the subject meets the termination criteria outlined in **Section 7.2**. It ends at 120 hours post SCD or ICU discharge, whichever comes first. Record the following data daily in the Study Follow-up Period unless otherwise noted:

- **Vital Signs/Physical Assessment**
 - Blood pressure, heart rate, temperature
 - Physical Exam (first 24 hours only)
 - Urine Output (from previous 24 hours)
 - Net fluid balance (from previous 24 hours)
- **Clinical Laboratory Tests (first 24 hours only)**
 - CBC with differential
 - BUN, Creatinine
 - Na, K, Cl, HCO₃, Ca, Mg, Ionized Ca, PO₄
- **Blood for Research**
 - Collect at 120 hours post SCD ± 6 hours
 - Blood sample will be sent to an outside laboratory (Innovative Biotherapies) for testing of biomarkers
- **Respiratory**
 - Status – Ventilator support (yes/no)
 - If on Vent: FiO₂
 - If on Vent with an arterial line: Arterial Blood Gas (first 24 hours only)
 - If on Vent without an arterial line: Arterial Blood Gas (if completed as standard of care, first 24 hours only)
 - ECMO Status (yes/no)
- **Renal Replacement Therapy status**
 - RRT status
- **Other (Event Driven)**
 - Microbiology/culture data
 - Adverse Events
 - Acknowledgement (yes/no) to antibacterial agents administered to the patient.
 - Concomitant treatments or procedures

